Randomization

At inclusion to the study protocol, each participant will be given consecutive numbers starting with number 1. To randomize participants to either placebo or MSCs we will use a table of random numbers, generated by a computer program (<http://www.randomization.com>). This table with

randomization numbers will only be available to specified personnel at the Tissue Center, Department of Clinical Immunology (Rigshospitalet).

Amount of ASCs required for injection

Based on published animal studies the amount of cells given for xerostomia to mice varies from 2×10^5 to 2×10^6 [23]. To convert these mice data to a realistic dose in humans we have extrapolated numbers based on the following data: The volume density of submandibular glands very closely approximates 1 mg/mm^3 ($1.06\text{-}1.07 \text{ mg/mm}^3$) [24]. In the mice studies on radiotherapy the mean gland weight was approximately 350 mg, which corresponds to an approximate volume of 350 mm^3 . Accordingly, the mouse dose pr. gland volume is approximately 2.86×10^5 to $2.86 \times 10^6 \text{ ASC/cm}^3$ gland (when calculated from either 1×10^5 to 1×10^6). The volume of the submandibular gland in human subjects after radiotherapy is $6.6\text{-}7.9 \text{ cm}^3$ [25]. This corresponds to an approximate dose pr. patient of between 1.9×10^6 to 2.3×10^6 , or 1.9×10^7 to 2.3×10^7 cells pr. submandibular gland. From the above assumptions, and in order not to administer an inadequate number of cells, we have chosen to proceed with the maximum dose corresponding to $2.8 \times 10^6 \text{ ASC/cm}^3$ gland, i.e. a maximum total dose per patient of approximately $4.48 \times 10^7 \text{ ASCs}$ (see below). However, to standardize the dose administered to patients, the amount administered will be standardized to the size of their submandibular glands, as described below.

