Injection of the ASCs or placebo-suspensions into submandibular glands will be performed by the principal investigator ([name]) under local anesthesia using ultrasonic guidance and sterile technique. The ASCs will be suspended in isotonic NaCl (0.9 mg/ml) and human albumin (HA) 1% to a final volume of 2 ml. Placebo will be 2 ml of isotonic NaCl (0.9 mg/ml) and HA 1%. After receiving the ASC-suspension or placebo-suspension, the surgeon (the principal investigator) will identify the submandibular glands and inject the ASC suspension. Calculation of injected number of ASCs pr. participant rests on the following calculation: $Suspension_{ml} = 2.8 \times 10^6 \frac{ASC}{cm^3} \times volume_{cm^3}$, where volume is the volume of the submandibular gland, and a gland-volume of approx. $7\text{-}8 \text{ cm}^3$ is the norm. Therefore, the amount of ASCs given to each participant will be approx. $2.8 \times 10^6 \frac{ASC}{cm^3} \times 8cm^3 \times 2 = 4.48 \times 10^6 \text{ ASCs}$ in total. If the expanded number of ASCs does not fulfil the above criteria, it is accepted to diminish the number to a minimum of 50% of the calculated dose.

Justification for patient population

In order to standardize the participant population, we choose to only include participants treated for a human papilloma virus (HPV)-positive oropharyngeal squamous cell carcinoma, and exclude patients with severe salivary gland hypofunction and already manifest or near-manifest xerostomia, as this population most likely will not benefit from this treatment. This will be assessed by a preliminary questionnaire and a subsequent saliva flow rate measurement before inclusion.

Eligibility criteria

Evaluation of eligibility criterias and consent forms are collected by the Primary Investigator.

Inclusion criteria:

- Previous radiotherapy for a T1-T2 and N0, N1 or N2a, HPV-positive oropharyngeal squamous cell carcinoma with bilateral irradiation of the neck
- 2 years follow-up without recurrence
- Clinically reduced salivation and hyposalivation, evaluated by a screening
 - Unstimulated whole saliva flow rate in the range of 0.05-0.20 ml/min
- Informed consent
- Grade 1-3 xerostomia as evaluated by the “Udvalg for Kliniske Undersøgelser” (UKU) side effect rating scale[26].

Exclusion criteria:

- Any cancer in the previous 2 years
- Ongoing xerogenic medications
- Any other diseases of the salivary glands, e.g. Sjögrens syndrome, sialolithiasis, etc.

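### The worked dosing example prints a total of 4.48×10^6 ASCs per participant, but its factors give 4.48×10^7, the total stated elsewhere in the same section

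*Combined protocol and SAP*

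**What the plan says.** The section Amount of ASCs required for injection converts mouse doses to a human dose per unit of gland volume. It chooses the upper end, 2.8×10^6 ASC/cm³, and states "a maximum total dose per patient of approximately $4.48 \times 10^7 \text{ ASCs}$ (see below"; the cross-reference leads to the worked calculation in the next paragraph. It adds that "the amount administered will be standardized to the size of their submandibular glands".

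That next paragraph sets out the dosing rule. The formula multiplies 2.8×10^6 ASC/cm³ by the gland volume. It is followed by an example for two glands of 8 cm³: "2.8 \times 10^6 \frac{ASC}{cm^3} \times 8cm^3 \times 2 = 4.48 \times 10^6 \text{ ASCs}$ in total". The next sentence deals with a shortfall in expansion: "it is accepted to diminish the number to a minimum of 50% of the calculated dose". The exclusion criteria use the same threshold, so a participant whose cells cannot be expanded to half of the calculated dose is excluded.

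The cells are suspended "to a final volume of 2 ml". The section on the surgical method for injection supplies this as two 1 ml syringes, with 0.5 ml placed in each of two areas of a gland.

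**The concern.** One section gives two totals per participant, 4.48×10^7 and 4.48×10^6, and the second is presented as the calculation behind the first. Both cannot be right. The wrong one is the result of an arithmetic line in the text that tells staff how to dose, so it is more than a background remark.

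The trial is described as first-in-man, has safety as its primary outcome and is meant to inform the design of later trials. The number of cells given is basic to reading any safety result. Anyone who takes the total from the worked example would report a tenth of the intended exposure. The plan also describes the trial as still recruiting, so on the text supplied a correction would serve the conduct of the trial as well as its report.

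**Working it through.** **Inputs, all from Amount of ASCs required for injection**

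- Chosen dose density: 2.8×10^6 ASC/cm³.
- Gland volume: 8 cm³ in the worked example, 7-8 cm³ given as the norm, 6.6-7.9 cm³ after radiotherapy.
- Glands treated: two.
- Mouse doses used in the conversion: 1×10^5 and 1×10^6 cells for a gland of about 350 mm³ (0.35 cm³).
- Smallest acceptable share of the calculated dose: 50%.

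**Step 1: the plan's worked example**

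Cells per gland = density × volume = 2.8×10^6 × 8 = 2.24×10^7.

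Participant total = 2 × 2.24×10^7 = 4.48×10^7.

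The example prints 4.48×10^6, and 4.48×10^7 / 4.48×10^6 = 10. The printed result does not follow from its factors. The total in the first paragraph, 4.48×10^7, does.

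**Step 2: does the rest of the derivation support 4.48×10^7?**

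Mouse densities: 1×10^5 / 0.35 = 2.86×10^5 and 1×10^6 / 0.35 = 2.86×10^6 ASC/cm³, as the plan states.

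Upper density over the post-radiotherapy volumes: 2.86×10^6 × 6.6 = 1.89×10^7 and 2.86×10^6 × 7.9 = 2.26×10^7. The plan prints 1.9×10^7 to 2.3×10^7, which agrees. These are amounts for one gland.

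Two-gland totals at the chosen 2.8×10^6 ASC/cm³:

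| Volume of each gland (cm³) | Total for two glands |
|---|---|
| 6.6 | 3.70×10^7 |
| 7.0 | 3.92×10^7 |
| 7.9 | 4.42×10^7 |
| 8.0 | 4.48×10^7 |

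Every volume that the plan mentions gives a total of order 10^7.

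**Step 3: can another reading produce 4.48×10^6?**

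Counting one gland only, at the smallest volume, gives 2.8×10^6 × 6.6 = 1.85×10^7, still well above the printed total. The printed value needs a density of 4.48×10^6 / (8 × 2) = 2.8×10^5 ASC/cm³. That is about the lower mouse-derived density, which the plan passes over so as not to give too few cells.

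**Step 4: the 50% minimum**

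For two 8 cm³ glands the calculated dose is 4.48×10^7, so the minimum is 0.5 × 4.48×10^7 = 2.24×10^7 in total.

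**The case against.** The best defence is that the printed total controls nothing. It is an approximate illustration at 8 cm³. The dose given follows each participant's gland size, and the correct total can be recovered from the factors in the same line and from the paragraph before it. The 50% minimum is tied to the calculated dose, which is the result of the rule and not the printed example. No part of the plan tells staff to check a preparation against the printed figure. All of this stands. It limits the consequence, but it does not make the stated dose right.

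A reader might infer more: that participants would receive a tenth of the intended cells, or that a preparation of 2.24×10^6 cells (half of the printed total) would pass the minimum. The documents do not support either inference. The volume-based rule produces neither preparation, and nothing shows that anyone was misdosed.

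A reader might also hold that the formula is faulty. It is introduced with "Calculation of injected number of ASCs pr. participant rests on the following calculation", yet it uses the volume of one gland and carries a millilitre label on its left side. That goes too far. With one 1 ml syringe per gland, the expression can be read as cells per ml of suspension for that gland, and the doubling in the example then gives the participant total. The wording is terse, but it can be read sensibly.

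The conversion paragraph has a smaller slip. It introduces its ranges with "This corresponds to an approximate dose pr. patient of between" and closes them with "cells pr. submandibular gland". The closing unit is the correct one.

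Finally, one exponent digit could have been misread when the PDF was converted. That cannot be excluded from the text supplied. It is a reason to check the original first.

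**Conclusion.** The point holds as an error in the stated dose. The worked example in the operative dosing text gives a participant total ten times too low: 4.48×10^6 instead of 4.48×10^7. It contradicts the total given in the same section. The direction is not in doubt, because the factors, the chosen density and the per-gland range all lead to 4.48×10^7.

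The conclusion rests on two assumptions: that the exponent was read correctly from the PDF, and that doses are prepared from the volume-based rule as the plan describes. On the second assumption the doses given and the 50% minimum are right, and the harm is confined to a wrong statement of exposure. The dose total does not enter the sample-size calculation.

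The correction should be made. The figure is the stated dose of a first-in-man safety trial, and it comes immediately before a threshold that also decides exclusion.

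**What to change.** 1. Check the original document. If it too prints 4.48×10^6 in the worked example, change it to 4.48×10^7.
2. Keep the formula per gland and state it in cells: cells for each gland = 2.8×10^6 ASC/cm³ × that gland's volume in cm³, suspended in that gland's own 1 ml syringe. State the participant total as the sum over the right and left glands. This keeps the density the same in both glands when their sizes differ, which an equal split of a pooled total would not.
3. State that the 50% minimum is taken from this calculated dose, for example 2.24×10^7 in total for two 8 cm³ glands.
4. Optionally, label the ranges in the conversion paragraph as per gland from the start.

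The cost is one exponent, a clearer formula and one or two labels. The chosen density, the stated maximum total, the number of patients and the visits are unchanged.

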Originally described more than 40 years ago, MSCs reside in almost all connective tissues [18]. More recently, there has been an increasing awareness that MSCs have a number of interesting secretory paracrine bystander characteristics including anti-inflammatory, anti-apoptotic, immunomodulatory, angiogenic and trophic (tissue-regenerating) properties. Notably, MSCs have shown promising results in preclinical studies for the treatment of xerostomia, including radiation-induced xerostomia [19].

The objectives of the current trial are to assess the safety and feasibility of autologous adipose tissue-derived MSCs administered for radiation-induced salivary gland hypofunction and

xerostomia in head and neck cancer patients. Head and neck cancer is the sixth most common malignancy worldwide, and the majority of these patients are due to advanced disease stage at presentation treated with chemo-, radiotherapy, or both [20,21]. The project can potentially help to develop a clinically relevant treatment option for the growing number of patients suffering from xerostomia after radiotherapy.

Methods and materials

Primary outcome

Primary outcome is safety, including adverse events (AEs) and severe adverse events (SAEs). All measures of AEs will be graded according to Common Terminology Criteria for Adverse Events (CTCAE) [22]. Since this is a local treatment with ASCs the primary safety measures are:

- Pain at injection site (Grade 1: Mild pain, grade 2: Moderate pain; limiting instrumental activities of daily living (ADL), grade 3: Severe pain; limiting self-care ADL)
- Oral discomfort (Grade 1: Mild discomfort; not interfering with oral intake, grade 2: Moderate pain; interfering with oral intake, 3: Disabling pain; tube feeding or total parental nutrition indicated)
- Infection (Grade 1: Localized; local intervention indicated, grade 2: Oral intervention indicated (antibiotic, antifungal, antiviral), grade 3: IV antibiotic, antifungal or antiviral indicated; or radiologic, endoscopic or operative intervention indicated, grade 4: life threatening consequences; urgent intervention needed)

Secondary outcomes

- Unstimulated and stimulated whole saliva and selective submandibular saliva flow rate and composition of saliva.
- Complaints of xerostomia as evaluated by a physician and patient questionnaire.
- Measurement of volume, fibrosis, and vascularisation change of submandibular glands based on magnetic resonance imaging (MRI).

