- Pregnancy or planned pregnancy within the next 2 years
- Breastfeeding
- Any other disease/condition judged by the investigator to be grounds for exclusion
- Treatment with anticoagulant that cannot be stopped during the intervention period
- Failure of expanding up to 50% of the calculated dose of ASC
- Withdrawal of informed consent

Criteria for withdrawal of subjects under study

- Pregnancy
- Infection of the transplanted site
- Allergy to local anesthetic
- Withdrawal of consent from participants
- In case of withdrawal or dropouts before assessment of efficacy patients will be replaced to ensure that a total of 30 patients complete the study.

Surgical method for mini-liposuction

The procedure is done in an outpatient setting, and performed under sterile conditions according to local guidelines. 6 ml of local anesthesia (lidocaine 1 %) is injected subcutaneously at two injection sites of the lateral abdomen. Two 5 mm incisions are then made and Klein's solution is injected with a blunt infiltrator through the incisions. The fatty tissue is harvested from the abdomen with a 3 mm blunt cannula 23 cm in length, coupled to the MonoJect 60 ml syringe with a blunt and Toomey tip (Teico Healthcare). The harvested lipoaspirate is sedimented in the syringe. Any oil layer at the top or aqueous layer at the bottom is removed. By this procedure the middle layer of fat tissue is obtained and will be transported in a sterile plastic bag for the isolation of ASCs.

Surgical method for submandibular gland biopsy

This procedure takes place in an outpatient settings. A biopsy will be taken 14 days before injecting the ASC and four months after injection. The biopsy procedure is carried out under sterile conditions; in local anesthesia with lidocaine with epinephrine 0.5% an ultra-sound-guided, core biopsy of one of the glands is taken. Participants are randomized for biopsy of either the right or left gland. Each biopsy will be fixed in 4% formalin and sent for histology.

Surgical method for injection of ASC or placebo in submandibular gland

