The procedure will be performed without local anesthesia in an outpatient setting. The surgeon will receive two syringes of the sterile ASC-suspension or placebo of each 1 ml (total of 2 ml). The suspensions are injected into each submandibular gland guided by ultrasound. The ASC-suspension will be deposited in two areas (superficial and deep lobe) with equal volume per site (0.5ml) to ensure equal distribution of the suspension. The subject will afterwards receive a small band aid,

which can be removed the same day. The participant will be administered over the counter pain relief.

Assessment of xerostomia and subjective treatment outcome

The subjective effect of the treatment is assessed by a 100 mm visual analogue scale of xerostomia filled out by the patient [27] and a physician-rated questionnaire [28], both carried out at baseline as well as one and four month after treatment (Figure 1).

Assessment of salivary flow rate and objective treatment outcome

Changes in the secretion rate of the unstimulated whole saliva in the oral cavity is probably the most important parameter for the biological development of xerostomia and accompanying pathological oral conditions. Whole saliva, e.g., the secretions from the major and minor salivary glands are mixed in the oral cavity. A precise determination of this value is crucial for the assessment of efficacy in this trial. For determination of the saliva flow rate, whole saliva will be collected between 2 p.m. and 3 p.m. for all collections to take the salivary diurnal variation into account. Participants will refrain from eating, drinking, smoking and oral hygiene for 2 hrs. prior to collection. After being seated upright in a chair, subjects relax for 5 min and are then instructed to make as few movements as possible, including swallowing, during the collection.

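### The printed total cell dose is one tenth of the product of its own factors, and two sections contradict each other on local anaesthesia for the injection

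*Combined protocol and SAP*

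**What the plan says.** **Cell number.** The section Amount of ASCs required for injection sets a rate of 2.8 × 10^6 ASC per cm^3 of gland and gives "a maximum total dose per patient of approximately $4.48 \times 10^7 \text{ ASCs". It adds that "the amount administered will be standardized to the size of their submandibular glands". The next paragraph repeats the rate as a formula, takes 8 cm^3 as the gland volume and counts two glands, and ends with "8cm^3 \times 2 = 4.48 \times 10^6 \text{ ASCs}$ in total". If expansion falls short, "it is accepted to diminish the number to a minimum of 50% of the calculated dose". The exclusion criteria include the matching item "Failure of expanding up to 50% of the calculated dose of ASC".

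**Anaesthesia.** The same section says the principal investigator injects ASCs or placebo "under local anesthesia using ultrasonic guidance and sterile technique". The section Surgical method for injection of ASC or placebo in submandibular gland says of that injection: "The procedure will be performed without local anesthesia in an outpatient setting".

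**Outcome affected.** Under Primary outcome, the first safety measure listed is "Pain at injection site (Grade 1: Mild pain, grade 2: Moderate pain; limiting instrumental activities of daily living", followed by the grade 3 definition.

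**The concern.** The worked example is where the plan says how many cells each participant will receive, and its total disagrees with both its own factors and the preceding paragraph. Anyone who prepares or reports from that total instead of the rule would be off by a factor of ten, in a trial described as first-in-man.

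The error would not necessarily look absurd to a reader. The plan extrapolates two dose levels from the mouse data, ten times apart, and says it proceeds with the higher. The level not chosen is 1.9 × 10^6 to 2.3 × 10^6 per gland, or 3.8 × 10^6 to 4.6 × 10^6 for two glands. The printed 4.48 × 10^6 falls inside that range.

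On anaesthesia, the two instructions are opposites and cannot both describe one procedure. If practice varied between participants, recorded injection-site pain would not be comparable across them. If practice was uniform, the comparison between arms would not be biased, but the reported pain frequency would still have to say which procedure it describes. The same holds for the Discussion's statement that the risk of pain, infection and bleeding is below 0.5% with similar procedures.

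**Working it through.** **Inputs**, all from Amount of ASCs required for injection: rate 2.8 × 10^6 ASC/cm^3; gland volume 8 cm^3 in the worked example (norm 7 to 8 cm^3; 6.6 to 7.9 cm^3 after radiotherapy); two glands; minimum accepted share 50%.

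**1. The plan's own product.** Total = rate × volume × glands.
- 2.8 × 10^6 × 8 × 2 = 4.48 × 10^7.
- Printed: 4.48 × 10^6. Ratio: 4.48 × 10^7 / 4.48 × 10^6 = 10.

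**2. Can another reading reproduce the printed figure?**
- 7 cm^3, two glands: 2.8 × 10^6 × 7 × 2 = 3.92 × 10^7.
- 8 cm^3, one gland: 2.8 × 10^6 × 8 = 2.24 × 10^7.
- Working back: 4.48 × 10^6 / 16 cm^3 = 2.8 × 10^5 ASC/cm^3, which is not the stated rate.

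No combination of the stated rate with the stated volumes and one or two glands gives 4.48 × 10^6.

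**3. Does the preceding paragraph agree with the rule?** Its upper per-gland range is reproduced from the unrounded rate: 2.86 × 10^6 × 6.6 = 1.89 × 10^7 and 2.86 × 10^6 × 7.9 = 2.26 × 10^7, against the stated 1.9 × 10^7 to 2.3 × 10^7. Its total of 4.48 × 10^7 equals the product in step 1.

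**4. Size at the cited post-radiotherapy volumes (two glands).**

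| Gland volume | Rule's dose | 50% minimum | Printed total as share of rule |
|---|---|---|---|
| 6.6 cm^3 | 3.70 × 10^7 | 1.85 × 10^7 | 12.1% |
| 7.9 cm^3 | 4.42 × 10^7 | 2.21 × 10^7 | 10.1% |
| 8 cm^3 (example) | 4.48 × 10^7 | 2.24 × 10^7 | 10.0% |

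**5. Against the plan's own minimum.** Half the rule's dose at mean gland volume v is 0.5 × 2.8 × 10^6 × v × 2 = 2.8 × 10^6 × v. Setting this equal to 4.48 × 10^6 gives v = 1.6 cm^3. Above that volume the printed total is below the 50% minimum. If the minimum were instead taken from the printed total, it would be 2.24 × 10^6 rather than 2.24 × 10^7.

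**6. Anaesthesia, side by side.** Both statements concern the injection of ASC or placebo into the submandibular glands; one says with local anaesthesia, the other without. The other mentions of local anaesthesia do not decide it. Those in Trial design and in the liposuction and biopsy sections concern other procedures. The withdrawal criterion on allergy to local anaesthetic could refer to either of those procedures.

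**7. Minor items.** The left side of the dose formula is labelled in ml, while the right side is a cell count. The vehicle is called isotonic at 0.9 mg/ml NaCl. Taking a molar mass of 58.44 g/mol and full dissociation, that is 0.9 / 58.44 = 15.4 mmol/l, or about 30.8 mOsm/l. The documents give no reference value for isotonicity, so this is only a prompt to check the label against the concentration.

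**The case against.** The strongest reply is that the rule is intact. Both paragraphs use the same rate, the number is scaled to each participant's gland volume, and the 50% minimum is a share of the calculated dose. The printed total is an approximate illustration at 8 cm^3, its error can be seen on the same line, and no text tells anyone to prepare cells from it. A dose calculated from the rule would not inherit the slip, and no eligibility decision under the written rule changes. All of that stands. The exponent may also have been lost in typesetting or in converting the file to text, and preparation documents outside this plan may be correct. Neither can be excluded, and a check of the source would settle it. Calling one total a maximum and the other approximate, however, cannot explain an exact tenfold gap with identical leading digits.

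On anaesthesia, the trial has one centre and one operator, which makes mixed practice less likely. Participants receive over-the-counter pain relief after the injection, and pain grades 2 and 3 are defined by limits on daily activities, so the link from anaesthesia to graded pain is less direct. These points weaken the case for bias but do not remove the contradiction. It is a conflict of words, not of digits, so a conversion error does not plausibly explain it, and no other section settles it.

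It is also fair to say that the unit label and the saline description are peripheral. The conclusion does not depend on them.

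**Conclusion.** The concern holds, with high confidence. The total in the worked example is one tenth of the product of its own factors and one tenth of the total in the preceding paragraph, while the per-volume rule is the same in both. The conflict lies in the printed total, not in the rule. At gland volumes of 6.6 to 7.9 cm^3 the printed total is 12% to 10% of the rule's dose. The instructions on local anaesthesia for the injection contradict each other outright.

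Nothing in the documents shows that anyone was misdosed or that anaesthesia practice varied, and uniform practice would leave the comparison between arms unbiased. The point must nevertheless be fixed. It concerns the stated dose in a first-in-man trial and the procedure behind the first-listed primary safety measure. The arithmetic assumes only the plan's stated rate and gland volumes and two glands treated. It does not establish which total or which anaesthesia instruction was intended.

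**What to change.** 1. Reconcile the total in the worked example with its own factors and with the total in the preceding paragraph. The statements that the dose and the 50% minimum are calculated per participant from gland volume can stay as they are.
2. Reconcile the two sections on local anaesthesia so that a single statement covers the injection for all participants in both arms.
3. Enrolment began in May 2015 and the plan describes the trial as recruiting. Before the safety analysis, check batch and procedure records for any participants already treated, to confirm the cell number given and the anaesthesia used, and report the injection-site pain frequency with that information.
4. In the same revision, correct the unit label on the dose formula and reconcile the description of the saline with its stated concentration.

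The cost is a text correction and a check of any existing records. Design, dosing rule and sample size do not change.
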